### Plasma:

PK Parameter	Definition
$C_{max,ss}$	Maximum observed concentration in plasma at steady-state.
$C_{ave,ss}$	Average concentration in plasma at steady-state calculated as the ratio of $AUC_{tau,ss}/24$ .
$C_{trough,ss}$	Drug trough concentration immediately before the next dose in plasma at steady-state.

PK Parameter	Definition
$T_{max,ss}$	Time of maximum observed concentration in plasma at steady-state.
$AUC_{tau,ss}$	Area under the concentration-time curve over a 24 hour dosing interval in plasma at steady-state, calculated using the linear up/log down rule.
$CL/F_{ss}^*$	Apparent total body clearance in plasma at steady-state, calculated as: Dose/ $AUC_{tau,ss}$ .

\*not calculated for 5-HVLX-gluc

Actual sampling times and actual midpoint times will be used for the estimation of all PK parameters in breast milk and plasma, respectively.

Analysis: Viloxazine and 5-HVLX-gluc breast milk and plasma PK parameters will be presented in data listings and summarized by analyte using descriptive statistics (n, mean, SD, CV, minimum, median, maximum, geometric mean, and geometric CV).  $T_{max}$  will be summarized using n, median, minimum, and maximum only.

## 9. Safety Analysis

All safety summaries and analyses will be based upon the Safety Population.

### 9.1 Adverse Events

An AE is defined as any untoward medical occurrence in a patient or clinical investigation subject administered a pharmaceutical product and which does not necessarily have to have a causal relationship with treatment.

A treatment-emergent AE (TEAE) is defined as an AE with a start date on or after the first dose of SM, or that worsened following first administration of SM. Adverse events are recorded only after SM has been administered; therefore, all AEs are treatment-emergent.

Suspected Adverse Drug Reactions (SADRs) are a subset of AEs for which there is evidence to suggest a causal relationship between the SM and the AE, i.e., there is a reasonable possibility that the SM caused the AE. Adverse Drug Reactions (ADRs) are a subset of all SADRs for which there is reason to conclude that the SM caused the event.

A serious AE (SAE) is defined as an AE or ADR if, in the view of either the investigator or Sponsor, it results in one of the following outcomes:

- Death

- Life-threatening AE (i.e., the subject was at immediate risk of death from the AE as it occurred. This does not include an event that, had it occurred in a more severe form or was allowed to continue, might have caused death.)
- In-patient hospitalization or prolongation of existing hospitalization
- Persistent or significant disability or incapacity or substantial disruption of the ability to conduct normal life functions
- A congenital anomaly or birth defect
- An important medical event

The AE's relationship to SM will be evaluated by the investigator. The following relationships will be collected on eCRF: definitely related, possibly related, unlikely related, or not related.

The AEs that are evaluated as definitely related or possibly related will be considered treatment-related AEs for summary purpose.

The severity of AEs will be classified by the investigator as mild, moderate, or severe.

An overall AE summary will be generated presenting the frequency and percentage of subjects and the number of AEs for the following:

- Any TEAE
- Any treatment-related TEAE
- Any moderate TEAE
- Any treatment-related moderate TEAE
- Any severe TEAE
- Any treatment-related severe TEAE
- Any SAE
- Any treatment-related SAE
- Any TEAE leading to study discontinuation
- Any TEAE leading to treatment discontinuation
- Any TEAE leading to treatment adjustment (including dose increased, dose reduced, or drug interrupted)
- Any death

All AEs will be coded using MedDRA version 26.0. The TEAEs will also be summarized by system organ class (SOC), PT, and by severity and relationship to SM.

The TEAE summary tables will be sorted by SOC and PT. System organ class will be displayed in descending order of overall frequency then alphabetically. Preferred term will be displayed in descending order of overall frequency and then alphabetically within SOC. A subject with 2 or more events within the same level of summarization will be counted only once in that level using

the most severe incident or most related incident. Percentages will be based on the number of subjects in the Safety Population.

All AEs will be presented in a data listing. Separate data listings will be generated for treatment-related AEs, SAEs, deaths, and AEs leading to treatment discontinuation.

## 9.2 Clinical Laboratory Evaluations

The hematology, serum chemistry, urinalysis, serology, pregnancy, and urine drug screen tests will be performed at the timepoints indicated in the schedule of assessments ([Section 13](#)).

All clinical laboratory test results will be presented in the data listings. Laboratory values that are outside of the normal reference range will be flagged in the data listings and presented in a separated listing.

The actual values and change from baseline values for hematology, serum chemistry, and urinalysis at each time point will be summarized for the Safety Population. Shift from baseline in terms of low/normal/high for hematology and serum chemistry tests, and in terms of normal/abnormal for urinalysis tests will be summarized for the Safety Population.

## 9.3 Vital Sign Measurements

Vital signs will include orthostatic systolic and diastolic blood pressure, pulse rate, respiratory rate, and oral temperature, and will be measured at the timepoints indicated in the schedule of assessments ([Section 13](#)).

All vital signs will be presented in a data listing and abnormal results will be presented in a separated data listing. Weight, height, and BMI will be presented in a separate data listing.

The normal reference range for vital signs is as below:

Position	Parameter	Predose	Postdose
Sitting/Standing	Temperature	96.0-99.8 °F / 35.6-37.7 °C	95.0-100.0 °F / 35.0-37.7 °C
	Respiratory Rate	10-20 breaths/min	10-20 breaths/min
	Pulse Rate	40-100 beats/min	40-120 beats/min
	Blood Pressure	90-140 mmHg / 50-90 mmHg	90-150 mmHg / 40-100 mmHg

The actual values and change from baseline values for orthostatic systolic and diastolic blood pressure, pulse rate, respiratory rate, oral temperature, and weight at each time point will be summarized for the Safety Population. The orthostatic changes for blood pressure and pulse rate will be calculated using the measurements at standing position minus the measurements at sitting position at the same timepoint. The orthostatic changes for respiratory rate and oral temperature

will also be calculated using the measurements at standing position minus the measurements at sitting position at the same timepoint if data permit.

#### **9.4 Physical Examinations**

The physical examination will include assessments of head, eyes, ears, nose, throat, skin, thyroid, neurological, lungs, cardiovascular, abdomen, lymph nodes, and musculoskeletal, and will be performed at the timepoints indicated in the schedule of assessments ([Section 13](#)). Any clinically significant findings during Screening will be recorded as medical history and any clinically significant abnormal findings during treatment will be recorded as an AE. At the EOS physical examination, only changes from Baseline will be noted.

All physical examination results will be presented in a data listing.

#### **9.5 Clinical Breast Examinations**

The clinical breast examination is a physical examination of each breast, including visual inspection of the skin and nipples, and an assessment of the underarms and collarbone area, and will be performed at the timepoints indicated in the schedule of assessments ([Section 13](#)). Any clinically significant findings during Screening and/or Baseline will be recorded as medical history and any clinically significant abnormal findings during or after treatment (after first dose of SM) will be recorded as an AE. Only changes from Baseline will be noted for the clinical breast examination at the EOS.

All clinical breast examination results will be presented in the physical examination data listing.

#### **9.6 Electrocardiograms**

The ECG will be recorded while the subject is resting in a supine position for at least 5 minutes.

Heart rate (HR), PR interval, QRS duration, RR interval, QT interval, QT interval corrected for heart rate using Fridericia's formula (QTcF), and interpretation of ECG will be captured on the eCRF.

Single 12-lead ECG will be performed at the timepoints indicated in the schedule of assessments ([Section 13](#)). Additional ECGs may be performed at other times if deemed necessary by the Principal/Site Investigator.

The actual values and changes from baseline values for numeric ECG data at each time point will be summarized for the Safety Population.

Shift from baseline in interpretation of ECG results will be summarized for the Safety Population using the frequency count and percentage of subjects in each category (normal, abnormal and not

clinically significant, abnormal and clinically significant, indeterminate, or not evaluable/unknown).

All ECG data will be presented in a data listing and abnormal results will be presented in a separated data listing.

The normal reference range for ECG results is as below:

Parameter	Screen/Pre-Dose	Post
HR	40-100 beats/min	40-120 beats/min
PR	120-220 ms	120-240 ms
QRS	>130 ms	80-120 ms
QTcF	<470 ms	<470 ms
QT	(already ranges for QTcF)	(already ranges for QTcF)
RR interval	(calculated off HR)	(calculated off HR)

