4 STUDY POPULATION

4.1 Number of Subjects

Up to 15 healthy, lactating women will be enrolled in the study.

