4.3 Exclusion Criteria

1. Participation in any other investigational study drug trial in which receipt of an investigational study drug within 30 days or 5 half-lives before Screening, whichever is longer.
2. Is unwilling or unable to comply with the Lifestyle guidelines presented in the protocol during the study period.
3. Has history or presence of clinically significant systemic disease (including psychological and psychiatric disorders).
4. Is currently using, or tests positive at Screening for cotinine, alcohol or drugs (opiates, methadone, cocaine, amphetamines [including ecstasy], barbiturates, PCP, benzodiazepines, and THC/cannabis).
5. Is pregnant (has positive serum pregnancy test at Screening) or becomes pregnant during study (has positive urine pregnancy test).
6. Has history of breast implants, breast augmentation, or breast reduction surgery.
7. Has history of mastitis within 30 days, breast cancer and/or has had a mastectomy or lumpectomy with the exception of a benign fibroma or lipoma removal at the investigator's discretion; and/or a clinically significant abnormality observed in either breast during a clinical breast exam at Screening or Admission (Day -1).
8. Has a history of alcohol use disorder within 1 year of Screening; or assessed by the PI as having regularly consumed alcohol exceeding 14 units per week (1 unit equals 340 mL of beer, 115 mL of wine, or 43 mL of spirits) within 1 year of Screening.
9. Is using recreational or illicit drug(s) (e.g., cannabis /tetrahydrocannabinol (THC), opiates, methadone, cocaine, amphetamines [including ecstasy], barbiturates, benzodiazepines) within 1 year of Screening.
10. Has clinically significant vital sign abnormalities (systolic blood pressure less than 90 or greater than 140 mmHg, diastolic blood pressure less than 60 or greater than 90 mmHg, or pulse rate (PR) less than 50 or greater than 100 bpm at Screening).

11. Has a clinical laboratory test values outside the reference range at Screening that, in the opinion of the investigator, are clinically significant, or any of the following:
 - Serum creatinine >1.5 times the upper limit of normal (ULN)
 - Serum total bilirubin >1.5 times ULN
 - Serum alanine aminotransferase (ALT) or aspartate aminotransferase (AST) >2 times ULN
12. Has a clinically significant ECG abnormalities at Screening, including:
 - PR interval >220 ms
 - QRS interval >130 ms
 - QTcF interval >470 ms

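### The SAP's pre-dose normal range for QRS (>130 ms) is the protocol's exclusion region, so a listing built on it would call every eligible screening QRS abnormal

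*SAP*

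**What the plan says.** SAP section 9.6 (Electrocardiograms) introduces a table with "The normal reference range for ECG results is as below". Its columns are Screen/Pre-Dose and Post. The QRS row is "QRS >130 ms 80-120 ms".

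Protocol section 4.3, exclusion criterion 12 (repeated in the synopsis), sets three interval limits that count as clinically significant abnormalities at Screening: PR above 220 ms, "QRS interval >130 ms" and "QTcF interval >470 ms".

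SAP section 9.6 plans these ECG outputs:

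- numeric summaries: "The actual values and changes from baseline values for numeric ECG data at each time point will be summarized for the Safety Population";
- a shift table: "Shift from baseline in interpretation of ECG results will be summarized for the Safety Population";
- listings: "All ECG data will be presented in a data listing and abnormal results will be presented in a separated data listing".

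The section does not say whether an abnormal result in the last of these means a value outside the table or an abnormal ECG interpretation from the eCRF.

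**The concern.** One set of values cannot be both the normal range and the excluded abnormality at the same visit. The QRS cell appears to be the exclusion limit carried over without reversing its direction.

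ECG is a named safety endpoint, and the reference table has no apparent use other than to decide which values are abnormal. Programmed literally, it would put the eligible screening QRS values into the abnormal-ECG listing and leave out a value that should have excluded the subject. The pre-dose entry also shares no values with the post-dose entry, so the QRS rows of the listing could not be compared before and after dosing.

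**Working it through.** No sample-size or power figure is involved. The check compares the stated ranges.

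**Step 1. Set exclusion 12 against the SAP's Screen/Pre-Dose column.**

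| Interval | Excluded (protocol 4.3, criterion 12) | Normal, Screen/Pre-Dose (SAP 9.6) | Relation |
|---|---|---|---|
| PR | >220 ms | 120-220 ms | excluded region lies outside normal |
| QTcF | >470 ms | <470 ms | excluded region lies outside normal |
| QRS | >130 ms | >130 ms | excluded region is the normal range |

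Two of the three limits were converted to the acceptable side. QRS was not.

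**Step 2. Compare eligible values with the pre-dose normal range.** Eligible means QRS ≤130 ms; normal as written means QRS >130 ms. These sets are exact complements. On a 1-ms grid from 40 to 200 ms:

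- eligible values (40-130 ms) that fall outside the stated normal range: 91 of 91;
- excluded values (131-200 ms) that fall inside it: 70 of 70.

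**Step 3. Compare the pre-dose and post-dose entries.** The sets >130 ms and 80-120 ms have no value in common. For a QRS that does not change (whole milliseconds):

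| QRS | Eligible? | Screening | Day 4 |
|---|---|---|---|
| below 80 ms | yes | abnormal | abnormal |
| 80-120 ms | yes | abnormal | normal |
| 121-130 ms | yes | abnormal | abnormal |
| above 130 ms | no | normal | abnormal |

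All three eligible bands are abnormal at Screening, and no unchanged value is normal at both visits.

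**Step 4. Count the values affected.** The schedules in both documents have one ECG at Screening and one on Day 4. Protocol section 4.1 states: "Up to 15 healthy, lactating women will be enrolled in the study". One screening QRS per subject gives up to 15 × 1 = 15 values, all listed as abnormal if the table drives the listing.

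**Step 5. See what reversing the direction alone would do.** With ≤130 ms as the pre-dose entry, 0 of the 91 eligible grid values are listed at Screening; with <130 ms, only a value of exactly 130 ms is. The mismatch with the post-dose entry remains. Under ≤130 ms, an unchanged QRS of 121-130 ms would be listed only after dosing, as would one below 80 ms if no lower limit is added. The cell therefore has to be reconciled with both exclusion 12 and the post-dose entry.

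**The case against.** The mismatch itself is hard to dispute. The case on the other side is about consequence.

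- **The table may not drive the listing.** Section 9.6 also collects an ECG interpretation with normal and abnormal categories, and protocol section 8.1.5.4 uses similar categories. If the listing follows the interpretation, no QRS row is wrong. This stands as a condition on the conclusion. The surrounding text favours a value-based reading: SAP section 9.2 sends laboratory values outside the reference range to a separate listing, section 9.3 pairs an abnormal-results listing with a reference-range table for vital signs, and the protocol synopsis plans to flag abnormal values. If the table does not drive the listing, it has no stated purpose.
- **Different limits before and after dosing are usual in this SAP.** Heart rate goes from 40-100 to 40-120 beats/min and PR from 120-220 to 120-240 ms. A difference alone is therefore no error. But those ranges widen after dosing and contain the pre-dose range; the two QRS ranges do not overlap at all.
- **An excludable value would rarely appear.** A subject with a screening QRS above 130 ms should not be dosed, so such a row would need an eligibility deviation or a later unscheduled pre-dose ECG. This is fair; the practical error is the listing of eligible values.
- **It could be a text-extraction fault.** A lost sign cannot be ruled out entirely, but the row is complete and the adjacent QTcF row kept its sign.
- **The error is small and would be noticed at output review.** It is small. But a silent correction would be undocumented, and the programmer has no stated limits to correct to.

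**Conclusion.** The Screen/Pre-Dose QRS entry is wrong as written: 1 of the 3 limits in exclusion 12 is entered as the exclusion region. On the assumption that the table defines abnormal for the separate listing, up to 15 of 15 eligible screening QRS values would be listed as abnormal, and the pre-dose and post-dose QRS rows would not be comparable.

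The reach is limited. The numeric summaries, the changes from baseline, the shift table by interpretation and every PK endpoint do not depend on this table. The values in the full ECG listing are also unaffected; if range-based flags are added there, as the synopsis may imply, those flags would carry the same error. The correction should be made, but nothing in the trial's main conclusions turns on it.

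**What to change.** Before programming, rewrite the Screen/Pre-Dose QRS cell in SAP section 9.6 as a normal range consistent with exclusion 12, and reconcile it with the post-dose entry of 80-120 ms. The sponsor must supply the intended limits, because the documents do not give them.

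In the same edit, add a sentence stating whether the separate abnormal-ECG listing takes values outside this table or ECGs with an abnormal interpretation.

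The cost is one table cell and one sentence, with no protocol change and no new data. If programming has already begun, make the same correction and document it.

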## 9.7 Prospective Assessment of Suicidality

Suicidality assessment will be performed using the Columbia Suicide Severity Rating Scale Baseline/Screening and Since Last Visit. The C-SSRS will be performed at the timepoints indicated in the schedule of assessments ([Section 13](#)).

The C-SSRS findings will be presented in a data listing.

## 10. Interim Analysis

No interim analysis is planned.

## 11. Changes in the Planned Analysis

There are no changes in the planned analyses stated in the protocol.

### 13. Schedule of Assessments

Table 13-1: Schedule of Events and Assessments

Study Visit	Visit 1	Visit 2				FPC	
Study Period	Screening	Admission	Treatment		EOS/ET		
Study Day (window)	-28 to -1	-1	1	2	3	4	11 (±2)
Signed informed consent	X						
Medical/Psychiatric/Maternal history a	X	X					
Demographics	X						
Height (BMI)	X						
Physical examination	X					X	
Clinical Breast Exam	X	X				X	
Serum pregnancy test	X	X					
Urine pregnancy test						X	
Serology	X						
Serum chemistry	X	X				X	
Hematology	X	X				X	
Urinalysis	X	X				X	
Urine drug screen b	X	X					
Vital signs and weight c	X	X	X	X	X	X	
12-lead ECG	X					X	
C-SSRS; Baseline/Screening	X						
C-SSRS; Since Last Visit		X				X	
Review eligibility criteria	X	X d					
Review adverse events e			X	X	X	X	X
Review concomitant medications	X	X	X	X	X	X	X
SM administration f			X	X	X		

Study Visit	Visit 1	Visit 2				FPC	
Study Period	Screening	Admission	Treatment		EOS/ET		
Study Day (window)	-28 to -1	-1	1	2	3	4	11 ( $\pm 2$ )
PK blood sampling g			X		X	X	
PK breast milk sampling h			X		X	X	
Non-PK breast milk sampling h		X	X	X			
Confinement		X	X	X	X		

Abbreviations: BMI = body mass index; C-SSRS = Columbia Suicide Severity Rating Scale; ECG = electrocardiogram; EOS = end of study; ET = Early Termination; FCP = follow-up phone call; PK = pharmacokinetics; SM = study medication

- a. Psychiatric (including Edinburgh Postnatal Depression Scale) and maternal (gestational age at delivery, stage of lactation, and length of time postpartum) information should be included. Medical/psychiatric history will be reviewed and updated as needed at Admission.
- b. Cotinine and urine or breath alcohol tests should be included.
- c. Vital signs include orthostatic blood pressure, pulse rate, respiratory rate, and oral temperature. Perform vital signs prior to each dose on Day 1, 2, and 3. Weight will not be recorded on Day 4.
- d. Inclusion/exclusion criteria should be reviewed prior to breast milk sampling on Day -1.
- e. Adverse event should be monitored throughout the study via safety assessments, observation, and unsolicited reporting. Any events that occur prior to SM dosing should be captured as medical history.
- f. SM should be administered at the same time in the morning ( $\pm 30$  min) of study Days 1, 2, and 3.
- g. See [Section 8.3](#) for full PK blood sample collection schedule.
- h. PK and Non-PK breast milk samples will be collect following the collection schedule in [Section 8.2](#). The volume and the start and end times of each breast milk sample will be recorded.
